Compare the serologic responses to cell culture-based quadrivalent influenza vaccine (ccIIV [Flucelvax]) versus live attenuated quadrivalent influenza vaccine (LAIV [FluMist]) in a randomized controlled trial (RCT) among racially diverse children/young adults 4-21 years of age. The primary endpoint is change in antibody titer. The secondary Aims are to: 1. Compare the immune responses between ccIIV and LAIV; 2. The nasal microbiome may both effect and be affected by vaccination (2019 only);

Methods: An unblinded, randomized controlled trial will be conducted by Pediatric and Family Medicine teams at the UPMC and the University of Pittsburgh. Randomization to either LAIV or ccIIV on a 1:1 ratio will be done in blocks of 4. Depending on funding, up to 240-260 will be randomized; assuming a 16% drop-out rate (21% in children under 9 and 11% in ages 9 and up) this would result in approximately 200 participants. Efforts will be made to recruit/include children 4-8 years and persons not vaccinated in 2019-20 for comparison of immune response to those previously vaccinated in 2019-20. Young persons aged 4-21 years without a contraindication to LAIV who plan to receive seasonal influenza vaccination at one of our recruiting sites are eligible to participate. The primary endpoints are change in antibody titers. Given that LAIV is known to produce limited IgG [4], other potential beneficial responses to nasal administration of intranasal LAIV compared to ccIIV will be examined as secondary endpoints, including changes in serum IgA. Titer levels will be log transformed and reported as seropositivity, mean fold rise (MFR) and seroconversion. Specimens will be collected on a subset of participants for cell-mediated immune responses to be studied at CDC and Pitt.

Introduction

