Compare the serologic responses to cell culture-based quadrivalent influenza vaccine (ccIV [Flucelvax]) versus live attenuated quadrivalent influenza vaccine (LAIV [FluMist]) in a randomized controlled trial (RCT) among racially diverse children/young adults 4-21 years of age. The primary endpoint is change in antibody titer.

a. Serology—based on hemagglutination inhibition assay (HAI) titers: Hypotheses: Mean fold rise (MFR) based on HAI titers and seroconversion will differ between LAIV and ccIV.

Secondary Aims:

1. Compare the immune responses between ccIV and LAIV.
2. The nasal microbiome may both effect and be affected by vaccination (2019 only)

B. Study Design and Methods

B.1 Study Design and population Years 1 and 2 combined

1. Total number of subjects to be enrolled at this site up to 480 enrolled over two years (of up to 650 screened)
2. Describe and explain the study design:
This study will be an unblinded randomized controlled trial of 200-220 (2019) and up to 260 (2020) children, adolescents and young adults to examine their immune response following influenza vaccination. For 2020, all participants will have a baseline draw and a Day 28 (range 21-35 days) blood draw. A subset of up to 120 participants ages 9-21 **only** will have a blood draw on Day 7 (range 6-9 days)
3. Describe the primary and secondary study endpoints:
Primary:
-Seroconversion based on hemagglutinin inhibition (HAI) titers
Secondary:
- Day 0 and Day 28 Seroprotection based on HAI titers
- Day 0 and Day 28 geometric mean comparisons of HAI titers

The overall purpose is to understand immune responses related to influenza vaccination and their determinants. We will also look at serum IgG and IgA, cell mediated immunity indices, transcriptomics, genomic, protonomic, cell-mediated immunity, nasal microbiome (2019 only) and/or past vaccine experience effects on the immune response to influenza vaccination.

B.2 Study Design and Population Year 2 2020-2021 only

This study will be a randomized controlled trial of up to 260 children, adolescents and young adults to examine their immune response following influenza vaccination. All participants will have a blood draw at baseline and at Day 28 (range 21-35 days). A subset (up to 120) of participants ages 9 -21 will have a blood draw at Day 7 (range 6-9 days).

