Upon consent, participants will be randomized to one of two vaccine types (LAIV or cclIV) using a 1:1 computer generated simple randomization scheme. Randomization block size will be conducted in sets of four (2 LAIV and 2 cclIV).

Table. Specimens to be collected for 2020

Age Group	Blood tube type	Day 0 visit	Day 7 post vax visit	Day 28 post vax visit	Total
4-8 years	SST Serology	5-10 mL	No visit	5-10 mL	10-20 mL
	CPT-PBMCs	4 mL	No visit	4 mL	8 mL
9-21 years	SST Serology	10 mL	--	10 mL	20 mL
	CPT-PBMCs on subset	24 mL	24 mL	24 mL	72 mL

B.2.4.1b Vaccination visit

All participants will receive influenza vaccine after the pre-vaccination blood draw according to their randomized influenza vaccine allocation. Both vaccines are FDA approved, licensed and recommended for these age groups. Vaccinations will be recorded in the EMR and Vaccine Information Sheets will be provided following standard clinical protocol. This visit may occur at the time of the enrollment visit provided that the vaccine to which the participant is randomized is available.

B.2--4.1c Blood draw procedures

All blood will be collected by trained personnel with experience drawing blood from children. The blood samples will be collected using Vacutainer tubes, appropriate for type of processing, and appropriately labeled with a uniform scheme (including study ID and collection time point).

Serum specimens will be aliquoted and frozen. Individual aliquots will be either shipped to CDC for analysis, analyzed by labs affiliated with the University of Pittsburgh or UPMC, or banked for future studies that might involve proteomics, immunology, transcriptomics, or genomics. .

B.2.4.2 Follow-up study visits

All participants will have a blood draw at Day 28 (range 21-35 days). A subset (up to 120) of participants ages 9 -21 will have a blood draw at Day 7 (range 6-9 days).

The amount of blood to be drawn at each timepoint is noted in the Table.

B.2.4.3 Specimen Processing and Sharing with Collaborators

[name] lab at the Rangos Research Building will process all blood specimens for storage and handling following standard protocols by trained study staff. Specimens will be shipped to CDC and CDC's chosen laboratory contractors as well as to other contracted laboratories for processing and analysis.

Flow cytometry results from CDC will be shared with Pitt so that further bioinformatics analyses can be conducted.

B. 3 Laboratory Methods

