IgD, CD95, CD11b, CD38, CD57, CD27, CD123, CD127, HLADR, KLRG1, CD45R0, CD154. With this panel we can identify granulocyte, monocyte, and lymphocyte subsets with high resolution. For example, this panel allows for identification of CD8+ T cells, NKT cells, CD4+ T cells, B cells, NK cells, and lineage negative ILC, further segregated by activation and memory markers. All of this information is derived from a single flow cytometry run on 5×10^6 cells.

Data are analyzed by multidimensional algorithms such as t-stochastic neighborhood embedding (tSNE) or sequential pattern discovery using equivalence classes (SPADE) to cluster cell types based on the full panel of antigens stained rather than typical two dimensional staining analyses. tSNE works by first creating a probability distribution that dictates the relationships between various neighboring data points in high-dimensional space. It then tries to recreate a low dimensional space (two dimensional plot) that follows that probability distribution as best as possible to segregate cells based on similarity of marker expression. SPADE uses a similar approach to determine relationships between individual cells, but relays this information as a two dimensional branching tree plot that indicates the degree of similarity between cells. These algorithms allow for identification in three dimensions of overlapping cell subsets in two dimensional space and consideration of multiple stains at the same time, with the potential to identify new cell subsets.

C. Statistical Analysis

Pre- and post- vaccination geometric mean antibody titers (GMT) will be \log_2 transformed and compared among participants who received LAIV or cclIV. The mean fold rise, seroconversion and seropositivity at Day 28 will be calculated.

Seroconversion will be defined as either a pre-vaccination HAI titer $<1:10$ and a post-vaccination HAI titer $\geq 1:40$ or a pre-vaccination HAI titer $\geq 1:10$ and a minimum four-fold rise in post-vaccination HAI antibody titer.

Fold-rise in HAI titers is the ratio of Day 28 log titers to Day 0 log titers and will be conducted with baseline titer as a covariate.

C.1 Power Analyses

Using a power calculation for a Chi square test with alpha set at 0.05 reveals the following:

Effect size	Final sample size	Power	Comments
0.3	90	.81	Fairly large effect size; unlikely to occur
0.3	81	.77	Fairly large effect size; assumes 10% failure to complete
0.1	81	.15	No power for small effect size

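### Section C defines fold-rise as a ratio of log titers, which is not a fold rise and does not agree with the titer-scale four-fold rule in the same section

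*Combined protocol and SAP*

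**What the plan says.** Section C gives the only formula for fold-rise in the document: "Fold-rise in HAI titers is the ratio of Day 28 log titers to Day 0 log titers". The same sentence adds that the analysis "will be conducted with baseline titer as a covariate". Earlier in that section, for participants with a detectable baseline, seroconversion requires "a minimum four-fold rise in post-vaccination HAI antibody titer", which is a ratio of titers.

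Mean fold rise (MFR) has a visible role:

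- The hypothesis under the Primary Aim (A. Specific Aims) reads "Mean fold rise (MFR) based on HAI titers and seroconversion will differ between LAIV and ccIV".
- Section C states "The mean fold rise, seroconversion and seropositivity at Day 28 will be calculated".
- The Methods paragraph of the opening summary states "Titer levels will be log transformed and reported as seropositivity, mean fold rise (MFR) and seroconversion".

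The endpoint list in B.1 does not include MFR. It gives seroconversion as primary, and seroprotection and geometric mean titer comparisons as secondary.

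**The concern.** The log of a quotient is the difference of the logs. Dividing one log titer by another gives a different quantity, which depends on where the participant started as well as on how far the titer rose. Two participants with the same true rise then receive different values if their baselines differ.

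An analyst who follows the sentence literally would report, for a measure named in the primary hypothesis, a number that is not a fold rise. It could not be set beside the four-fold seroconversion criterion or beside fold rises computed in the usual way. The end of C.1 also plans analyses by prior vaccine history, which is not randomised. The document does not say whether MFR will be used there. If it is, a baseline-dependent measure would be harder still to interpret.

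**Working it through.** **Inputs.** The fold-rise definition, the four-fold rule and the log2 transformation come from Section C. The document gives no titer data, so the baselines below are illustrative. The value 5 for a titer below 1:10 is an assumption.

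**The plan's own figures.** The only computed figures in Section C are in the C.1 power table. Chi-square power at alpha 0.05 uses noncentrality N × w². The degrees of freedom are not stated; 1 is assumed, and 2 or 3 do not reproduce the table.

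| w | N | N × w² | Recomputed | Stated |
|---|---|---|---|---|
| 0.3 | 90 | 8.10 | 0.812 | .81 |
| 0.3 | 81 | 7.29 | 0.770 | .77 |
| 0.1 | 81 | 0.81 | 0.147 | .15 |
| 0.2 | 200 | 8.00 | 0.807 | .81 |
| 0.1 | 200 | 2.00 | 0.293 | .29 |

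All five rows reproduce, and none uses the fold-rise definition.

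**Fold-rise as written.** For baseline titer a and true fold rise k, the stated quantity is

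log(k·a) / log(a) = 1 + log(k) / log(a).

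The log base cancels, so specifying log2 does not help. The baseline a stays in the denominator. For example, with k = 4 and a = 10: 1 + 0.602/1 = 1.602.

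| Baseline | Four-fold rise (k = 4) | Eight-fold rise (k = 8) |
|---|---|---|
| 1:5 (assumed) | 1.861 | 2.292 |
| 1:10 | 1.602 | 1.903 |
| 1:40 | 1.376 | 1.564 |
| 1:160 | 1.273 | 1.410 |

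Order can reverse between participants. A rise from 1:160 to 1:1280 (eight-fold) scores 1.41, below a rise from 1:10 to 1:40 (four-fold) at 1.60.

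**Averaged.** Take five pairs that each rise exactly four-fold, from baselines 10, 20, 40, 80 and 160. The individual values are 1.602, 1.463, 1.376, 1.316 and 1.273, with mean 1.41. If the sentence means the mean log titer at Day 28 over the mean log titer at Day 0, the result is 7.32/5.32 = 1.38. The true geometric mean fold rise is 4.00.

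**Dependence on coding.** A fold rise does not change if titers are rescaled. The ratio of logs does. With titers coded as titer/5, the same four-fold rise scores 3.00, 2.00, 1.67 and 1.50 from baselines 10, 20, 40 and 80.

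**Against the four-fold rule.** A literal value of 4 requires a Day 28 titer of a⁴:

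- From 1:10: 10⁴ = 10,000, where the seroconversion rule needs 4 × 10 = 40.
- From 1:40: 40⁴ = 2,560,000, where the rule needs 4 × 40 = 160.

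**With the usual definition.** 2^(log2 Day 28 − log2 Day 0) gives 4.00 for every four-fold pair above, at any baseline.

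**The case against.** The strongest reply is that this is a slip of wording. The sentence speaks of a rise in titers, the seroconversion rule beside it uses four-fold correctly, and the plan calls for log transformation, so most statisticians would compute a difference of logs. That is plausible, but no other text gives a formula, and an analyst has only this sentence to follow.

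Several limits on the point stand:

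- Seroconversion has its own complete titer-scale definition and does not use the fold-rise sentence. The inconsistency is one of terms. No threshold of 4 is applied to MFR, so the a⁴ figures show only how far apart the two meanings are.
- At a fixed baseline above 1, the ratio of logs increases with the true fold rise, and no change scores 1 at every baseline. The order reversal therefore arises only between participants with different baselines. The planned covariate deals with part of this, but it does not turn the result into a fold rise.
- Allocation is random (B.2.4.1a: "using a 1:1 computer generated simple randomization scheme"), and this alone keeps the between-arm test valid.
- Any effect on power could go either way, depending on how the arm difference varies with baseline. The document does not give this.
- MFR is absent from the B.1 endpoint list, although the Primary Aim names it.
- The value given to titers below 1:10 is a separate and minor matter.

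**Conclusion.** The concern holds. As written, the formula does not give a fold rise, and it is inconsistent with the way Section C uses four-fold in the seroconversion definition. A true four-fold rise would be recorded as 1.60, 1.38 or 1.27 from baselines of 1:10, 1:40 or 1:160. These values are exact and need no assumption beyond the choice of illustrative baselines.

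The consequence is confined to the meaning of the reported MFR. No bias in the test, no loss of power and no effect on seroconversion, seroprotection or the sample size is claimed. Correct MFRs can be computed from the same titers. It should be corrected because MFR belongs to the primary hypothesis and the correction is trivial.

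**What to change.** Replace the sentence in Section C with:

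> Fold-rise is the Day 28 titer divided by the Day 0 titer; MFR = 2^(mean of log2 Day 28 − log2 Day 0). Arms are compared on the log2 difference with baseline log2 titer as covariate, back-transformed to an MFR ratio with 95% CI.

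The definition is the essential part. The second sentence puts the comparison and the covariate on the same scale and says how the result is reported.

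As a minor addition, state the number assigned to titers below 1:10. MFR needs it, and so does the B.1 secondary endpoint, "Day 0 and Day 28 geometric mean comparisons of HAI titers". If a share p of titers at a visit is below 1:10, using 10 instead of 5 multiplies that visit's geometric mean by 2^p. That is 1.07 at p = 10% and 1.41 at p = 50%; the range of p is assumed. The MFR changes by 2^(p at Day 28 − p at Day 0).

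The cost is one sentence and one clause, with no new data and no change to the sample size or the seroconversion analysis. If a difference of logs was always intended, only the wording changes.

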0.2	200	.81	Good power for moderate effect size
0.1	200	.29	No power for small effect size

<https://www.anzmtg.org/stats/PowerCalculator/PowerChiSquare>

If funding is available for the full sample, analyses based on prior 2019-20 vaccine history (none, egg-based, cell-based) will provide additional insight into vaccine immunogenicity.

D. Human Subjects

D.1. Consent

Participants in this study will provide written consent (parents and young adults) and assent (children/teens) as applicable for specimen collection, influenza vaccination, and medical record review.

Further details regarding data privacy and protection of human subjects are provided in the IRB application document.

D.2. Participant Compensation

Participants will be compensated for each visit:

- First visit = \$35 plus \$5 travel for a total of \$40
- Second visit on subset = \$25 plus \$5 travel for a total of \$30
- Final visit = \$45 plus \$5 travel for a total of \$50

The maximum possible payment will be \$90 (two visits)-\$120 (three visits). If a separate vaccine visit is required, participants will be paid \$30 for the blood draw and enrollment visit and \$10 for a separate vaccine visit.

D.3. Threats to study and contingencies

In the event of a late start, some aspects of recruitment may be impacted: (1) PBMCs are time-consuming to process, leading to a limited throughput; thus, the sample size for PBMCs is constrained by starting later. (2) vaccination in the community is likely to start early, due to vaccination by community pharmacies and to mass purchase by UPMC; later recruitment is more difficult because some will have already been vaccinated.

Contingency plans: In the event of a late start, several contingencies will be used. First, a greater emphasis will be given to recruiting young adults, who are less likely to have been vaccinated early. Second, if one vaccine is delayed, then persons may be recruited per the randomization scheme and those randomized to the missing vaccine may have their baseline blood drawn but be asked to return for the rest of the study once the vaccine is available. Third, given that quality processing of the PBMCs is time consuming with limited throughput, overall target sample sizes may be reduced.

D.4 Timeline

	Aug	Sept- Nov	Dec	Jan	Feb-May	June-July
Prep, Supplies, Train						
Enroll, vaccinate, draw blood, process specimens						
Organize and ship to CDC (or Battelle) lab						
Conduct initial HAI						
Advanced Lab assays						

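### Section C names no between-arm test or covariates for primary seroconversion; a pre-specified adjusted analysis would probably be more efficient than the unadjusted chi-square behind the power table

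*Combined protocol and SAP*

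**What the plan says.** Section B.1 gives the primary endpoint as "Seroconversion based on hemagglutinin inhibition (HAI) titers". The hypothesis under the Primary Aim (Section A) is wider: "Mean fold rise (MFR) based on HAI titers and seroconversion will differ between LAIV and ccIV".

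Section C is the analysis section. On seroconversion it gives the definition and this sentence: "The mean fold rise, seroconversion and seropositivity at Day 28 will be calculated". It states no test, model, effect measure or covariates for comparing the arms on seroconversion. Covariate adjustment appears once, in the sentence on fold-rise, which "will be conducted with baseline titer as a covariate".

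A test is named only in C.1, for the sample size: "Using a power calculation for a Chi square test with alpha set at 0.05". The row for the full sample (effect size 0.2, final N 200, power .81) is described as "Good power for moderate effect size".

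Three likely prognostic variables are available. Day 0 blood is drawn from every participant, age is an eligibility item, and vaccination history comes from medical or registry records (B.2.1, B.2.4.1a). Allocation is 1:1 in blocks of four, with no stratification factors stated. The end of C.1 reserves prior 2019-20 vaccine history for additional analyses if funding allows.

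**The concern.** The plan adjusts fold-rise for baseline titer but does not carry the adjustment over to the listed primary endpoint, whose definition branches on the pre-vaccination titer. The Introduction names age, antibody landscape and prior vaccine history as factors in vaccine effectiveness or response. The 2020 sample is mixed on these by design: about half are returning vaccinated participants, and new recruits are prioritized if aged 4-8 or if aged 9-21 and unvaccinated in 2019-20.

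Two things are at stake. If the covariates are prognostic, an unadjusted comparison gives up precision on the primary endpoint, in a trial with power .81 at effect size 0.2. And because Section C fixes no model, the choice between an adjusted and an unadjusted analysis could be made after the data are seen, in an unblinded trial.

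**Working it through.** **1. Reproduce the plan's powers.** C.1 does not define its effect size. I assume Cohen's w, 1 degree of freedom and N as the total. Power is then the probability that a noncentral chi-square with noncentrality N·w² exceeds 3.84.

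| w | N | N·w² | Computed | Stated |
|---|---|---|---|---|
| 0.3 | 90 | 8.10 | 0.812 | .81 |
| 0.3 | 81 | 7.29 | 0.770 | .77 |
| 0.1 | 81 | 0.81 | 0.147 | .15 |
| 0.2 | 200 | 8.00 | 0.807 | .81 |
| 0.1 | 200 | 2.00 | 0.293 | .29 |

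All five match. Reading N as per arm gives 0.979 for the fourth row, and 2 or 3 degrees of freedom give 0.718 or 0.654, so those readings are excluded. The table describes an unadjusted two-arm comparison of a binary outcome.

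**2. Power with covariates, by formula.** Let R² be the share of variance in seroconversion that the covariates explain. The noncentrality becomes approximately N·w²/(1−R²). R² is my assumption, because the documents give no value. For w = 0.2 and N = 200:

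| R² | 8/(1−R²) | Power |
|---|---|---|
| 0 | 8.00 | 0.807 |
| 0.05 | 8.42 | 0.827 |
| 0.10 | 8.89 | 0.846 |
| 0.20 | 10.00 | 0.885 |
| 0.30 | 11.43 | 0.922 |

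The gain is about 2 to 11 points. At w = 0.1 the same R² of 0.30 moves power only from 0.293 to 0.394, so adjustment does not rescue a small effect.

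**3. Check by simulation.** The formula charges nothing for estimating coefficients, so I also use simulated trials: 4,000 per setting, 60% v 40% seroconversion (which is w = 0.2 at equal allocation, since 0.2/(2×√(0.5×0.5)) = 0.2), one prognostic covariate and two with no effect. Entries are unadjusted chi-square v the Wald test of arm in the adjusted logistic model.

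| R² (approx.) | N = 200 | N = 82 |
|---|---|---|
| 0 | 0.822 v 0.808 | 0.475 v 0.444 |
| 0.05 | 0.824 v 0.834 | 0.478 v 0.454 |
| 0.17 | 0.831 v 0.874 | 0.460 v 0.485 |
| 0.29 | 0.826 v 0.916 | 0.481 v 0.561 |

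With useless covariates the loss is 0.822 − 0.808 = 0.014 at N = 200 and 0.475 − 0.444 = 0.031 at N = 82. At N = 82 a weak covariate (R² 0.05) still leaves a small net loss. N = 82 stands in for the 81-90 rows of C.1, but at w = 0.2, not those rows' 0.3 or 0.1.

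**4. Type I error.** At N = 200, with 40% or 13.7% seroconverting in both arms, the adjusted logistic test rejected in 0.046-0.054 of null trials and the standardized risk difference in 0.052-0.062.

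**The case against.** **The chi-square is not stated to be the primary analysis.** This is right. A reader might infer that the plan commits to an unadjusted chi-square for seroconversion. C.1 names it only as the basis of a power calculation, and Section C is silent. What stands is that it is the only applicable test in the documents.

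**Part of the primary aim is already adjusted.** Also right: fold-rise belongs to the primary hypothesis and uses baseline titer. The gap concerns seroconversion only.

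**The unadjusted test is valid.** Right again. A reader might infer that chance imbalance biases the result. Randomization, even unstratified, protects the test's validity. Adjustment buys precision.

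**The gain is not free.** A reader might infer that adjustment always raises power. It does not if the covariates are weak, above all in the small sample that C.1 allows for. Low response rates matter too: with an assumed 10% seroconverting in both arms and N = 82, an adjusted likelihood-ratio test rejects in about 0.06-0.07 of null trials.

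**The direction of the baseline effect does not follow from the definition.** A reader might infer that seroconversion is by definition harder from a high baseline. A titer below 1:10 must reach 1:40, more than a four-fold rise, while from 1:10 upward exactly four-fold suffices. The case for adjustment needs baseline to be predictive, in either direction. How predictive it is remains an assumption.

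**Conclusion.** The point holds as one of efficiency and pre-specification. Section C leaves the primary seroconversion comparison without a test, effect measure or covariates, and the only default that the documents offer is unadjusted. At N = 200 and w = 0.2, adjustment would take power from 0.81 to about 0.83-0.92 if the covariates explain 5-30% of outcome variance, and would cost about 1 point if they explain none. Near N = 82 the cost is about 3 points.

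These figures rest on reading the effect size as Cohen's w and on an assumed range for R². The documents do not support saying that the stated powers are wrong, that the unadjusted test is biased, or that the gain is assured.

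**What to change.** In Section C, state the primary seroconversion analysis as follows.

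- **Model:** for each vaccine strain, a logistic regression on randomized arm with that strain's log2 baseline titer, age group (4-8, 9-21) and prior-season vaccination as covariates. The prior season is 2018-19 for 2019 enrollees and 2019-20 for 2020 enrollees.
- **Effect measure:** the standardized risk difference with its confidence interval. This avoids the adjusted odds ratio, which does not estimate the same quantity as the marginal difference between arms. State which test gives the primary p-value.
- **Details to settle in advance:** the functional form for baseline titer, the value assigned to titers below 1:10, and the handling of missing vaccination history.
- **Sensitivity analysis:** the unadjusted chi-square.
- **Small sample:** if the final size is near the 81-90 rows of C.1, adjust for baseline titer only. This keeps the model small when events may be few, though it need not remove the small loss if baseline is uninformative. Fix the sample-size threshold for this rule beforehand.

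The power table can stay as the unadjusted reference. The cost is SAP wording, one model per strain, and some work on incomplete vaccination records. No new data collection is needed.
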